6.2.3. Disease Control Rate

DCR will be calculated for brain metastasis per mRECIST v1.1, extracranial lesion response per RECIST v1.1 and global response along with corresponding exact Clopper-Pearson 2-sided 95% CI.

6.2.4. Duration of Response

DOR will be calculated for patients with a confirmed response (CR or PR) for brain metastasis per mRECIST v1.1, extracranial per RECIST v1.1 and global response (brain metastasis and extracranial lesions) as follows:

$$\text{DOR (months)} = (\text{date of event or censoring} - \text{date of first CR or PR} + 1) / 30.4375$$

If a patient with a CR or PR did not have an event at the time of the analysis cutoff or with an event more than 16 weeks (for the first 11 cycles after treatment start date) or 24 weeks (after Cycle 11) after the last adequate tumor assessment, the patient will be censored on the date of the last adequate tumor assessment that documented no progression. In addition, if a new anticancer therapy is started prior to an event, the patient will be censored on the date of the last adequate tumor assessment that documented no progression prior to the start of the new anticancer therapy.

Adequate post-baseline assessment are defined in [Section 5.2.10](#).

The censoring and event date options to be considered for DOR analysis are presented in [Table 3](#).

Kaplan-Meier estimates will be presented together with a summary of associated statistics including the median DOR time with 2-sided 95% CI. Details are provided in [Section 5.2.14](#). DOR rates at 3, 6, 9, 12 and 15 months will be estimated with corresponding 2-sided 95% CIs.

In addition, a plot of time to and duration of response for patients with a confirmed response (swimmer plot) will be created.

Table 3: PFS and DOR Outcome and Event Dates

Situation	Date of Progression/Censoring	Outcome
No adequate baseline assessment ^a	Date of first dose ^a	Censored ^a
PD or death - after at most one missing or inadequate post-baseline tumor assessment, or - ≤8 weeks ((±3-day window) after date of first dose	Date of PD or death	Event
PD or death - after ≥2 missing or inadequate post-baseline tumor assessment, or	Date of last adequate tumor assessment ^b documenting no PD prior to new anticancer therapy, or missed tumor assessments	Censored
No PD		
New anticancer therapy given prior to PD or death		
^a This criterion only applies to PFS censoring. If the participant dies ≤8 weeks after date of first dose and did not initiate new anticancer therapy, the death is an event with date on death date (8 weeks is 2 times the length of the first 2 tumor assessment intervals). ^b If there are no adequate post-baseline assessments prior to the PD or death, then the time without adequate assessment should be measured from the date of first dose; if the criteria is met, the censoring will be on the date of first dose.		

6.2.5. Progression-free Survival

PFS will be calculated for brain metastasis per mRECIST v1.1 and global assessment (brain metastasis and extracranial lesions) as follows:

$$\text{PFS (months)} = (\text{date of event or censoring} - \text{date of first dose} + 1) / 30.4375$$

The algorithm to derive the outcome, event dates and reasons for censoring for PFS will be the same as that to derive those for the analysis of DOR (Section 6.2.4). The censoring and event date options to be considered for PFS analysis are presented in Table 3.

PFS time will be estimated using the same Kaplan-Meier method as described for DOR in Section 6.2.4. The PFS rate at 3, 6, 9, 12, 15 and 18 months will be estimated with corresponding 2-sided 95% CIs.

Frequency (number and percentage) of participants with each event type (PD or death) and censoring reasons will be presented along with the overall event and censor rates. Reasons for censoring will be summarized according to the categories in Table 4.

In addition, time to progression/censoring, event, and censoring reasons will be listed.

Table 4: PFS Censoring Reasons and Hierarchy

Hierarchy	Condition	Censoring Reason
1	No adequate baseline assessment	No adequate baseline assessment
2	Start of new anticancer therapy before event	Start of new anticancer therapy
3	Event after 2 or more missing or inadequate post-baseline tumor assessment/start date	Event after missing or inadequate assessments
4	No event and [withdrawal of consent date \geq date of first dose OR End of study (EOS) = Subject refused further follow-up]	Withdrawal of consent
5	No event and lost to follow-up in any disposition page	Lost to follow-up
6	No event and [EOS present OR disposition page for any phase after screening says participant will not continue into any subsequent phase of the study] and no adequate post-baseline tumor assessment	No adequate post-baseline tumor assessment
7	No event and none of the conditions in the prior hierarchy are met	Ongoing without an event

6.2.6. Overall Survival

OS will be calculated in months as follows:

$$\text{OS (months)} = (\text{date of death or censoring} - \text{date of first dose} + 1) / 30.4375$$

OS time will be estimated using the same Kaplan-Meier method as described for DOR in [Section 6.2.4](#). The OS rate at 6, 12, 18, 24, 30 and 36 months will be estimated with corresponding 2-sided 95% CIs.

Frequency (number and percentage) of patients with death events and censoring reasons will be presented by cohort along with the overall event and censor rates. The event and censoring reasons are as follows:

- Death:
 - Death due to COVID-19.
- Ongoing and no death.
- Withdrawal of consent.
- Lost to follow-up.

The OS time or censoring time and the reasons for censoring will also be presented in a patient listing.

6.2.7. Brain Metastasis Response Rate for Safety Lead-in

BMRR per mRECIST v1.1 will also be calculated for Dose-determining Set patients in the Safety Lead-in portion of the study. An exact two-sided 95% CI of BMRR will be reported.

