6.6. High-dose Safety Assessment

After 9 evaluable patients in the Safety Lead-in have completed one 28-day cycle of treatment, safety assessments will be conducted. All toxicities will be assessed for severity by the Investigator using CTCAE v4.03. Evaluable patients for the Safety Lead-in cohort must have either:

- experienced a DLT (Table 7) or
- received at least 75% of the planned cumulative dose of both study drugs during Cycle 1.

The Sponsor and participating Investigators will perform ongoing reviews of patient safety data through regular teleconferences approximately weekly during the Safety Lead-in. Once 9 evaluable patients are available for assessment, the Sponsor will convene a joint teleconference with participating Investigators. If the high-dose treatment is found safe based on 9 evaluable patients, subsequent patients will be randomized 1:1 to receive either the standard or high-dose treatment. If the high-dose treatment is determined not to be safe, enrollment will proceed with the standard-dose treatment as outlined in Section 4.1. The high-dose treatment will be considered safe if the rate of DLTs (Table 7) observed in the first cycle of treatment in the Safety Lead-in is $< 33\%$.

Table 7. Criteria for Defining Dose-limiting Toxicities

DLT Definition
A DLT is defined as any AE or laboratory abnormality that is not explained by underlying disease, disease progression, intercurrent illness, or concomitant therapies that either meets the criteria described below or results in the inability to tolerate at least 75% of the planned dose of binimetinib or encorafenib during Cycle 1.
Specific DLT Criteria
Cardiac disorders 
 • Absolute decrease of LVEF > 10% compared to baseline and the LVEF is below the institution's LLN • LV systolic dysfunction Grade ≥ 3 • Other cardiac disorders Grade ≥ 3
Vascular disorders 
 • Grade 3 hypertension for > 14 consecutive days • Grade 4 hypertension
Skin and subcutaneous tissue disorders^a 
 • Rash, hand foot skin reaction (HFSR) or photosensitivity CTCAE Grade 3 for > 14 consecutive days despite maximal skin toxicity treatment (as per local practice) • Rash, HFSR or photosensitivity CTCAE Grade 4

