6.11. Replacement of Patients

Patients may be replaced for any of the following reasons:

- During the Safety Lead-in, any patient who receives < 75% of the planned cumulative dose of either encorafenib or binimetinib during Cycle 1 for any reason other than a DLT (e.g., not evaluable for a DLT [Table 7]) may be replaced to ensure a minimum number of evaluable patients.
- Patients who do not meet the eligibility requirements of the study may be replaced.
- Patients for whom the *BRAFV600* mutation status is not confirmed by central laboratory may be replaced. This includes either an Indeterminate or a No Mutation *BRAFV600* Detected result.

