8.4.2.7. Brain Metastasis Response Rate for Safety Lead-in

Brain metastasis response rate per mRECIST v1.1 will also be calculated for Dose-determining Set patients in the Safety Lead-in portion of the study. An exact two-sided 95% CI of BMRR will be reported.

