3. ENDPOINTS AND BASELINE VARIABLES: DEFINITIONS AND CONVENTIONS

3.1. Safety Lead-in

3.1.1. Primary Endpoint

The primary endpoint for the Safety Lead-in is incidence of DLTs estimated based on data from DLT-evaluable patients during Cycle 1. A DLT is defined as any AE or laboratory abnormality (unexplained by underlying disease, disease progression, intercurrent illness, or concomitant therapies) that either meets the criteria described in the study protocol (Table 7) or results in the inability to tolerate at least 75% of the planned dose of binimetinib or encorafenib during Cycle 1.

3.2. Phase 2

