4. ANALYSIS SETS (POPULATIONS FOR ANALYSIS)

Data for all patients will be assessed to determine if patients meet the criteria for inclusion in each analysis population prior to releasing the database and classifications will be documented per standard operating procedures.

Patient Analysis Set	Description
Enrolled	All patients who sign the informed consent form (ICF). Potential participants who are screened for the purpose of determining eligibility for the study, but do not participate in the study, are not considered enrolled.
Dose-determining Set	All patients enrolled in the high-dose treatment arm in the Safety Lead-in who complete one 28-day cycle of treatment and receive at least 75% of the planned cumulative dose of both study drugs or discontinue treatment because of DLT.
Full Analysis Set (FAS)	The FAS includes all patients who receive at least 1 dose of any study drug in the Phase 2 portion of the study.
Efficacy Set	
The Efficacy Set includes all FAS patients who receive at least 1 dose of any study drug in the Phase 2 portion of the study and have their BRAFV600 mutation status confirmed by central laboratory.
 
Unless otherwise specified, the Efficacy Set will be the default analysis set used for all efficacy analyses.

Safety Set	The Safety Set includes all patients who receive at least 1 dose of any study drug. Unless otherwise specified, the Safety Set will be the default analysis set used for all safety analyses.
PK Set	The PK Set includes all patients who receive at least 1 dose of any study drug and have at least 1 PK blood collection after the first dose of study drug with associated bioanalytical results. The PKS will be used for summaries and listings of PK data.
CCI	[REDACTED]

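### Safety Lead-in BMRR uses the Dose-determining Set, which can leave out treated patients who die of or stop for disease in Cycle 1; report it in all treated Lead-in patients

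*SAP*

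**What the plan says.** Lead-in BMRR is a listed secondary endpoint. SAP 6.2.7 fixes its population: "BMRR per mRECIST v1.1 will also be calculated for Dose-determining Set patients in the Safety Lead-in portion of the study". Protocol 8.4.2.7 agrees: it "will also be calculated for Dose-determining Set patients in the Safety Lead-in portion of the study". Both ask for an exact two-sided 95% CI.

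SAP section 4 limits the Dose-determining Set to high-dose Lead-in patients "who complete one 28-day cycle of treatment and receive at least 75% of the planned cumulative dose of both study drugs". The only other way into the set is given by a further clause: "or discontinue treatment because of DLT". Protocol Table 15 gives the same definition.

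What counts as a DLT decides who enters by the second route. Protocol Table 7 (section 6.6) requires an event "not explained by underlying disease, disease progression, intercurrent illness" or concomitant therapy. SAP 3.1.1 repeats the restriction: "unexplained by underlying disease, disease progression, intercurrent illness, or concomitant therapies".

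Protocol 6.11 covers Lead-in patients who receive under 75% of either drug in Cycle 1 "for any reason other than a DLT". They "may be replaced to ensure a minimum number of evaluable patients".

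In Phase 2 the rule differs. The FAS needs one dose of any study drug, and the Efficacy Set adds central BRAF confirmation. SAP 6.1.2 divides by everyone in the Efficacy Set for the cohort, and lists early death without a post-baseline scan among the reasons for a Not Evaluable result. Both sets are confined to Phase 2.

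**The concern.** The Dose-determining Set was built to estimate a toxicity rate. For that purpose it is reasonable to set aside a patient who had too little drug, for reasons unrelated to toxicity, to be informative about DLTs.

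For a response rate the same rule selects on what happened after treatment began. A patient who dies of melanoma or stops for it within 28 days is a treatment failure with a known outcome, not a patient with missing information. Leaving that patient out, and possibly enrolling another instead, makes the Lead-in BMRR a rate among those who got through Cycle 1 or stopped for a DLT.

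At stake is how the high-dose response rate will be read. The regimen was not taken into Phase 2, so this rate is what a reader of the report will look to for brain activity at 300 mg BID. The Phase 2 rates in the same report handle an early death differently.

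**Working it through.** **Inputs**

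- Evaluable Lead-in patients: 9, with 3 DLTs (SAP section 2).
- Treated Lead-in patients outside the set: not given. Call this k and take 0 to 3 as an assumption.
- Lead-in responders: not given. Call this x.
- First scheduled post-baseline scan: Cycle 2 Day 1 (Protocol Table 3).
- Confirmation: two determinations at least 4 weeks apart (SAP 6.1.2).

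**The plan's own figures.** The documents state no figure for Lead-in BMRR. The Lead-in figures they do state are the operating characteristics in SAP Table 2, where the probability of declaring the dose toxic is P(X ≥ 3) for X ~ Binomial(9, p). At p = 0.30 this is 1 − (0.7⁹ + 9·0.3·0.7⁸ + 36·0.3²·0.7⁷) = 1 − (0.0404 + 0.1556 + 0.2668) = 0.537, as printed. The full column reproduces (0.053, 0.262, 0.537, 0.768, 0.910). The DLT rule is not in question.

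**Are the excluded disease failures non-responders?** On schedule, the first scan comes after day 28 and confirmation at least 28 days later. A patient who dies in Cycle 1 therefore cannot have a confirmed response on the planned scans. For a patient with brain progression, best overall response closes at progression. I treat all Cycle 1 disease failures as non-responders. The remote exception is a patient stopped for extracranial or clinical progression whose brain lesions shrank and were still confirmed.

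**Effect of leaving them out.** The planned rate is x/9 and the all-treated rate is x/(9 + k). Exact 95% CIs are in brackets.

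| x | k = 0 | k = 1 | k = 2 | k = 3 |
|---|---|---|---|---|
| 3 | 33.3% (7.5–70.1) | 30.0% (6.7–65.2) | 27.3% (6.0–61.0) | 25.0% (5.5–57.2) |
| 4 | 44.4% (13.7–78.8) | 40.0% (12.2–73.8) | 36.4% (10.9–69.2) | 33.3% (9.9–65.1) |
| 6 | 66.7% (29.9–92.5) | 60.0% (26.2–87.8) | 54.5% (23.4–83.3) | 50.0% (21.1–78.9) |

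If a share d of treated patients is excluded and none respond, the planned rate is the all-treated rate times 1/(1 − d). With d = 10%, 40% becomes 44.4%.

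**The other direction.** The set also drops patients below 75% of dose for non-DLT reasons unrelated to melanoma, such as intercurrent illness. Such a patient may resume and respond. One excluded responder gives 3/9 = 33.3% against 4/10 = 40.0%, or 4/9 = 44.4% against 5/10 = 50.0%.

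In general, let r of the k excluded patients be responders. The planned rate exceeds the all-treated rate when x/9 > (x + r)/(9 + k), that is, when xk > 9r, or r/k < x/9. One excluded failure together with one excluded responder gives 3/9 = 33.3% against 4/11 = 36.4%, so the net direction depends on who was excluded.

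**Does another analysis supply the all-treated rate?** The repeat of key efficacy analyses in the FAS (SAP section 6) does not reach the Lead-in, because the FAS is a Phase 2 set. SAP 6.5.2.1 reports Lead-in disposition and the number in each analysis set, and SAP 6.6.2 tabulates deaths within 30 days of first dose. These show how many patients were left out, but give no response rate that includes them.

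**The case against.** The strongest reply is that nothing shows the problem occurred. The documents describe 9 Lead-in patients and 9 evaluable patients, and replacement is optional. If all treated patients were evaluable, the two denominators are the same. A reader might infer from the definition that the Lead-in BMRR is in fact biased upward. The documents do not support that: the number excluded is unknown, it may be zero, and exclusions unrelated to disease can pull the other way.

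A reader might also infer that the set removes anyone who progresses in Cycle 1. It does not. The first scheduled scan follows Cycle 1, Protocol 6.8 allows treatment to continue after progression in one compartment only, and a patient who completes the cycle with enough drug stays in the set and counts as a non-responder. Patients who stop for a DLT also stay in. The gap concerns only patients whose disease ends dosing within the first 28 days, in a population that enters asymptomatic with ECOG 0 or 1.

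A third reply is that little depends on the number. SAP 5.1.1.1 sets no hypothesis for the Lead-in, the decision on the high dose rested on DLTs, no comparison with Phase 2 is planned, and at 3/9 the exact interval runs from 7.5% to 70.1%, far wider than any shift shown above. This stands, and it limits the point to a modest one.

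Finally, SAP version 2.0 was written with the DLT results known in an open-label study, so switching the denominator now could itself look post hoc. That is a fair reason to keep the planned figure visible beside the all-treated one. It does not justify leaving the all-treated figure out.

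**Conclusion.** The point holds as a defect in the choice of analysis set. The plan defines the denominator of a response endpoint by post-baseline events that can exclude early disease failures, while Phase 2 BMRR keeps such patients.

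If one to three early failures were excluded, the overstatement would be 3.3 to 8.3 percentage points at 3 responders and 4.4 to 11.1 points at 4. These sizes rest on assumed counts of responders and exclusions, and on all excluded patients being non-responders. With no exclusions the effect is zero; with excluded responders it can reverse.

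It would go too far to call this rate the trial's only efficacy evidence on 300 mg BID, because exploratory objectives and analyses are redacted. What can be said is that the unredacted text contains no all-treated Lead-in BMRR. The DLT conclusion, the Phase 2 test and the sample size are unaffected.

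**What to change.** In SAP 6.2.7 and Protocol 8.4.2.7:

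- Report Lead-in BMRR with its exact two-sided 95% CI in all Lead-in patients who received at least one dose of any study drug, counting every patient without a confirmed response as a non-responder.
- State how many Lead-in patients were treated, and how many fell outside the Dose-determining Set, with reasons.
- Keep the Dose-determining Set for the DLT analysis. BMRR in that set may be shown alongside as supplementary, which preserves the figure now planned.

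The cost is a short text change in each document and no new data. The downside is that the reported rate may be slightly lower.

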6.3. Other Secondary Endpoints

6.3.1. Pharmacokinetic Analysis

Plasma concentrations and PK parameters will be determined for encorafenib and its metabolite (LHY746) and binimetinib and its metabolite (AR00426032). PK summaries will be presented by treatment arm for patients in the PK set. In the following, Day y of Cycle x will be abbreviated as CxDy. C1D1 is defined as single dose (ie, first dose) and C1D15 is defined as multiple dose.

If a patient experiences emesis after dosing on C1D15, a full PK sampling schedule will be implemented on C2D1. In this situation, the C2D1 data will be summarized in PK tables and summary figures along with other patients' C1D15 data, and the C1D15 data for the affected patient will only be listed for information. Throughout the following text, all references to C1D15 includes C2D1 records in patients experiencing emesis on C1D15 rather than their C1D15 data.

6.3.1.1. Plasma Concentrations of Encorafenib, LHY746, Binimetinib and AR00426032

Plasma concentrations of encorafenib, LHY746, binimetinib and AR00426032 will be quantitated at the time points indicated in Table 5:

Table 5: Pharmacokinetic Blood Sampling Times

Study Visit	Timing of Sample	Allowed Window ^a
C1D1	0.5 hours postdose	±5 min
	1.5 hours postdose	±5 min
	3 hours postdose	±10 min
	6 hours postdose	±20 min
C1D15	Predose	-30 min
	0.5 hours postdose	±5 min
	1.5 hours postdose	±5 min
	3 hours postdose	±10 min
	6 hours postdose	±20 min
C2D1 ^b	Predose	-30 min
C3D1	Predose	-30 min

^a Predose samples must be within 30 minutes of, but before, the following dose.

^b When more sampling is performed on C2D1 due to emesis on C1D15, the sample times and windows will be the same as for C1D15.

All plasma concentration values of each analyte for each patient in the PK set will be included in the bioanalytical plasma concentration listings. Individual concentration records will be flagged for the affected visit if any of the following occur on the day of PK sampling:

- a. Patient had vomiting:
 - within 4 hours following study drug administration on the day of PK sampling for post-dose samples (C1D1, C1D15 and C2D1 when more sampling is performed on that day due to emesis on C1D15); or
 - at any time over the preceding 24 hours for pre-dose samples (C1D15, C2D1 and C3D1).
- b. Prescription dosing was not performed for at least 4 consecutive days prior to C1D15, C2D1 or C3D1).
- c. Patient received a higher or lower dose compared to planned treatment
- d. PK sampling time was outside the allowed window (as shown in [Table 5](#)) or the elapsed time was not calculable.

The plasma concentrations of encorafenib, LHY746, binimetinib and AR00426032 will be summarized by dose, treatment cohort or arm and combined arms as applicable for all nominal time points, including predose (trough) concentrations for C2D1 and C3D1, using the following descriptive statistics: n (number of patients with non-missing values), m (number of non-zero [ie, > below the limit of quantification (BLQ)] concentrations), arithmetic mean, standard deviation, coefficient of variation (CV), geometric mean, geometric CV, minimum, median and maximum. An individual concentration-time data point may be excluded from the calculation of summary statistics if any of the above flags [a-d] apply. Concentrations below the BLQ will be set to zero for calculation of all summary statistics; geometric mean and geometric CV will set to missing if at least one BLQ value is included in the data being summarized. The arithmetic mean with standard deviation plasma concentration-versus-time profiles will be presented graphically for each analyte using both linear and semi-logarithmic scales by treatment arm on C1D1 and C1D15. Individual plasma concentration-time profiles (with median overlaid) will also be presented graphically using linear and semi-logarithmic scales by treatment arm and study day. For ease of presentation, nominal times will be used to present results in summary figures; for individual figures, actual times will be used.

